#### Improvement in clinical status

The numbers and percentages of responders will be calculated up to Day 15 and up to Day 29 respectively. It will be presented by treatment group together with the difference in response rates.

#### Clinical status over time

The 9-point ordinal scale will be summarized (mean, median, standard deviation, minimum, maximum, frequencies and percentages in each category) will be summarized by visit (including a time point for data from early discharge) and treatment group.

A staged barchart illustrating the percentage of participants in each category of the 9-point ordinal scale will be provided. Treatment groups will be presented next to each other. This will be provided for Day 15 and Day 29.

The 9-point ordinal scale will also be plotted using a heat map with one row representing one patient and the score from baseline up to Day 29 visit will be shown by time using one unique color for each level of scale. The heat map will be plotted for each treatment group, within which patients will be sorted by the 9-point ordinal scale from high to low and by visit. The time when discharged from hospital will also be flagged on the plot. Values imputed by LOCF will be indicated by a different pattern (e.g. stripes) but the same color.

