### 1.3 Study objectives

**Table 1-1 Study objectives**

Objective(s)	Endpoint(s)
Primary Objective(s) 
 
To evaluate the effect of DFV890 in addition to SoC, compared with SoC alone, on the Acute Physiology and Chronic Health Evaluation II (APACHE II) score
 
	Endpoint(s) for primary objective(s) 
 
APACHE II severity of disease score on Day 15 or on day of discharge (whichever is earlier) with worst case imputation for death
 

Secondary Objective(s) 
 
To evaluate the effect of DFV890 in addition to SoC, compared with SoC alone, on inflammatory status
 
To evaluate the effect of DFV890 in addition to SoC, compared with SoC alone, on clinical status
 
	Endpoint(s) for secondary objective(s) 
 
Serum C-reactive protein (CRP) levels
 
 Endpoints based on the 9-point ordinal scale: 
 
Survival without the need for invasive mechanical ventilation at Days 15 and 29
 
At least one level improvement in clinical status at Days 15 and 29
 
Clinical status over time
 

 
To evaluate the safety of DFV890 in addition to SoC, compared with SoC alone
 
	
 
Number of participants with Adverse Events (AE), Serious Adverse Events (SAE), clinically significant changes in laboratory measures, and vital signs
 

Commercially Confidential Information

[figure not shown]

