## **6.2 Secondary objectives**

### **6.2.1 Variables**

The following variables and corresponding objectives are classified as secondary pharmacodynamic endpoints and will be evaluated for their effect of DFV890 in addition to SoC compared with SoC alone:

- On inflammatory status: Serum C-reactive protein (CRP) levels

- On clinical status: Endpoints based on the 9-point ordinal scale:
  - Survival without the need for invasive mechanical ventilation at Days 15 and 29: defined by a 9-point ordinal scale score of  $< 6$  points at all time points
  - At least one level improvement in clinical status at Days 15 and 29: defined as improvement of  $\geq 1$  in the 9-point ordinal scale score of the screening value – Day 15 or Day 29 score respectively.
  - Clinical status over time

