### **6.2.3 Statistical model, assumptions and hypotheses**

#### **CRP**

CRP levels are assumed to follow a log-normal distribution. Thus the log-transformed CRP data will be analyzed by fitting an MMRM model. Treatment, visit and their interaction as well as the three stratification factors will be included as fixed factors and log-transformed baseline CRP as a covariate. Interactions between visit and each of the terms in the model will also be included. To model the dependency of observations an unstructured variance-covariance matrix will be fitted.

The analysis will be performed on the PD analysis set. All available values at all scheduled visits (excluding discharge or early discharge visits) up to Day 29 will be included in this analysis. The back-transformed geometric means for both treatment groups as well as the geometric mean ratios (DFV890 in addition to SoC vs SoC alone) will be reported together with 90% confidence intervals (CIs) for each visit. The 1-sided p-value for the overall treatment factor will be reported.

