#### **Survival without the need for invasive mechanical ventilation**

Kaplan-Meier graphs with separate lines by treatment group will be provided for a graphical presentation. Censoring events will be death and discontinuation from the study.

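### Clinical status over time is a named secondary endpoint, but Section 6.2 plans no between-arm effect estimate on the full 9-point scale

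*SAP*

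**What the plan says.** Table 1-1 (SAP Section 1.3) states the secondary objective: "To evaluate the effect of DFV890 in addition to SoC, compared with SoC alone, on clinical status". Section 6.2.1 lists three endpoints on the 9-point scale.

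- "Survival without the need for invasive mechanical ventilation at Days 15 and 29", defined as a score below 6 at every time point.
- "At least one level improvement in clinical status at Days 15 and 29", defined as a gain of one level or more from the screening score.
- Clinical status over time.

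For each of the first two, Section 6.2.2 plans numbers and percentages of responders and adds: "It will be presented by treatment group together with the difference in response rates". No confidence interval, test or covariate adjustment is named. For the third: "The 9-point ordinal scale will be summarized (mean, median, standard deviation, minimum, maximum, frequencies and percentages in each category", by visit and treatment group, with bar charts at Days 15 and 29 and a patient-level heat map.

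Section 6.2.3, which holds the secondary models, covers CRP only: "Thus the log-transformed CRP data will be analyzed by fitting an MMRM model". Section 6.2.5 adds one display for the ventilation endpoint: "Kaplan-Meier graphs with separate lines by treatment group will be provided for a graphical presentation". No hazard ratio or test goes with it.

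**The concern.** The objective asks for an effect relative to SoC. One of its three endpoints keeps all nine levels, and that endpoint has no effect measure. The reader of the study report will get two columns of summaries and no estimate of how far apart they are.

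The two endpoints that do have a contrast use little of the scale. The ventilation cut puts scores 0 to 5 together, so a patient at home without limitations counts the same as one in hospital on high-flow oxygen. It also puts ventilation together with death. The improvement cut counts a move from 4 to 3 the same as a move from 4 to 1, and counts no change the same as death. If DFV890 shifts patients by various amounts along the scale, these contrasts will be imprecise and the full-scale data will go unsummarised. By-arm means do not fill the gap, because they treat the levels, with death as 8, as equally spaced.

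The trial is open-label. An ordinal method chosen after the data are seen would carry less weight than one fixed before database lock.

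**Working it through.** **Is there an estimate elsewhere in the text?** Going through Section 6.2 endpoint by endpoint:

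| Endpoint | Planned between-arm quantity | Interval or test |
|---|---|---|
| CRP | geometric mean ratio from MMRM | 90% CI, 1-sided p-value |
| Ventilation-free survival | difference in response rates; Kaplan-Meier graph | none |
| Improvement of at least one level | difference in response rates | none |
| Clinical status over time | none | none |

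Section 6.2.3 shows no redaction mark. Sections 6.1.9 and 6.3 are redacted, so an ordinal analysis there cannot be ruled out. The endpoint is a secondary one, however, and its own section contains none.

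**What could be lost?** The SAP shows no sample size, effect size or category distribution, so there is no planned figure to reproduce. Everything below is assumed, except the 1:1 allocation (Section 1.4) and the one-sided 10% level. That level is borrowed from the primary endpoint (Section 6.1.3), because none is set for clinical status.

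*Information kept by a cut.* Under a common odds ratio, the efficiency of a cut relative to the full scale is 3p(1−p) / (1 − Σpᵢ³). Here p is the mean probability on one side of the cut and pᵢ are the mean category probabilities over both arms. Take control probabilities for scores 0–8 of 2, 18, 25, 12, 15, 6, 7, 5, 10% and an odds ratio of 2.0.

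- Score <6: control 0.78, odds 0.78/0.22 = 3.545. Doubled, this is 7.09, so treated = 7.09/8.09 = 0.876 and p = 0.828. With Σpᵢ³ = 0.037, efficiency = 3 × 0.828 × 0.172 / 0.963 = 0.44.
- Score <4, which is improvement from a baseline of 4: 0.57 versus 0.726, so p = 0.648. Efficiency = 3 × 0.648 × 0.352 / 0.963 = 0.71.

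Over three control distributions and odds ratios of 1.5 and 2.0, efficiency ran from 0.40 to 0.64 for score <6 and from 0.43 to 0.76 for the improvement-type cuts.

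*Power at 70 per arm, odds ratio 1.8.* Three other control distributions (scores 0–8, %) were simulated, with baseline 4 in 60% and 5 in 40%:

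- A: 3, 22, 35, 5, 9, 5, 4, 5, 12
- B: 5, 35, 30, 5, 7, 3, 3, 4, 8
- C: 2, 12, 26, 8, 15, 10, 6, 8, 13

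The cuts were tested by a two-proportion z-test and the full scale by a tie-corrected Wilcoxon test. Ranges cover repeated runs of 4,000 to 20,000 trials.

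| Control | Score <6 | Improvement | Full scale |
|---|---|---|---|
| A | 51–52% | 59–60% | 74–75% |
| B | 44–45% | 51–53% | 73–74% |
| C | 55–56% | 64–65% | 75% |

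**Does the advantage hold for other effects?** Same three distributions, 70 per arm.

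- *Effect only on ventilation and death* (scores 6–8 cut by 40%, moved to 3–5). Full scale: about 18, 14 and 28%. Score <6: about 52, 44 and 61–63%. The ranking reverses.
- *Odds ratio of 1.8 at the higher thresholds, but the split among scores 0, 1 and 2 the same in both arms.* Full scale: about 58, 47 and 70%. Improvement cut: about 60, 53 and 64%. The advantage is gone in A, reversed in B and kept in C. Scores 0–2 hold 60, 70 and 40% of the assumed controls, so in A and B much of the gain comes from those levels.

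**Limits of the approximation.** The simulated ventilation endpoint is a single Day 15 score below 6, whereas the SAP requires it at all time points. The simulated outcome does not depend on baseline score, whereas the improvement endpoint is a change from screening.

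**The case against.** The strongest reply is that nothing here contradicts anything. The two response rates are not arbitrary dichotomies. Table 1-1 names them as endpoints, and any rationale for them belongs in the protocol. Describing secondary endpoints in a Phase 2 trial whose formal test is on APACHE II is a legitimate choice. The full scale is also reported: category frequencies appear by visit and arm, and an unadjusted odds ratio could be worked out from them.

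Most of that stands. It rules out a stronger reading that a reader might infer, namely that the SAP answers the clinical-status question with clearly less power than its data allow. The documents do not support that reading, for three reasons. No test is planned for the cuts, so no planned power is lost. The one-sided 10% level is set for the primary objective only. The size and even the direction of the difference depend on an assumed effect pattern.

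The core gap remains. An endpoint listed under an objective to evaluate an effect has no effect estimate. A figure derived by readers from frequency tables would be unadjusted for baseline score and stratification factors, and not prespecified.

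**Conclusion.** The point holds as an omission that is cheap to repair. Section 6.2 gives clinical status over time no between-arm estimate, and the two contrasts that exist on the scale have no interval.

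If the effect is a roughly common shift across levels, the cuts keep about 40–76% of the full scale's information. In the 70-per-arm illustration this means 73–75% power for the full scale against 51–65% and 44–56% for the cuts. These figures rest on assumed sample size, odds ratio and distributions. They do not carry over to an effect confined to ventilation and death, where the score <6 cut does better, or to one that leaves the ambulatory levels unseparated. The full-scale estimate should therefore complement the two response rates and not replace them. The primary analysis is unaffected.

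**What to change.** In SAP Section 6.2.3, under clinical status at Day 15 and at Day 29, add:

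- A proportional-odds model with treatment, the three stratification factors and the baseline 9-point score, on all randomised participants. Report the common odds ratio with its 90% CI as a secondary estimate, with no claim of formal testing.
- A stratified Wilcoxon (van Elteren) result in case proportional odds does not hold.
- A sensitivity analysis that merges scores 0–2. The missing-data rule in Section 6.2.1 sets some post-discharge scores to 2, so part of the separation at that end is fixed by rule.

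Keep both response rates as secondary endpoints in their own right.

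The cost is about one paragraph and a standard model. No new data are needed, because the existing rules impute death and carry scores forward to Day 29. The downsides are reliance on the proportional-odds assumption and one more secondary estimate to report.

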### **6.2.3 Statistical model, assumptions and hypotheses**

#### **CRP**

CRP levels are assumed to follow a log-normal distribution. Thus the log-transformed CRP data will be analyzed by fitting an MMRM model. Treatment, visit and their interaction as well as the three stratification factors will be included as fixed factors and log-transformed baseline CRP as a covariate. Interactions between visit and each of the terms in the model will also be included. To model the dependency of observations an unstructured variance-covariance matrix will be fitted.

The analysis will be performed on the PD analysis set. All available values at all scheduled visits (excluding discharge or early discharge visits) up to Day 29 will be included in this analysis. The back-transformed geometric means for both treatment groups as well as the geometric mean ratios (DFV890 in addition to SoC vs SoC alone) will be reported together with 90% confidence intervals (CIs) for each visit. The 1-sided p-value for the overall treatment factor will be reported.

### **6.2.4 Model checking procedures**

#### **CRP**

The appropriateness of the log-normality assumption of CRP values will be assessed by graphical mean e.g. residual plots.

### **6.2.5 Graphical presentation of results**

#### **CRP**

Estimated geometric mean CRP +/- SE will be plotted over time by treatment group. The estimated geometric mean ratio to baseline in CRP +/- SE will also be presented.

#### **Survival without the need for invasive mechanical ventilation**

Kaplan-Meier graphs with separate lines by treatment group will be provided for a graphical presentation. Censoring events will be death and discontinuation from the study.

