3. **Follow-up** (Day 16-29): After completion of the 14 day- treatment period, participants will be observed until Day 29 or discharged from hospital, whichever is sooner. Study assessments to be conducted every 2 days for hospitalized participants. If participants are discharged from hospital prior to Day 29, a study visit conducted by telephone will occur on Day 29 (all other visits between discharge and Day 29 can be omitted).
4. **30-day safety follow-up assessment** (Day 45): A follow-up visit for safety will be conducted by telephone.

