### Missing data

For the clinical status 9-point ordinal scale missing values will be handled as follows:

- For participants who died prior to Day 29: The score for death will be imputed for all visits following the death up to and including Day 29.
- For all other participants: LOCF will be applied up to and including Day 29. Following discharge or early discharge LOCF will be applied to all intermediate visits. In case the value reported for the (early) discharge visit does not reflect that the patient is ambulatory from now on (i.e. score  $\geq 3$ ), it will be set to the highest ambulatory score i.e. a value of 2 starting from the next scheduled visit.

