#### Survival without the need for invasive mechanical ventilation

The numbers and percentages of responders will be calculated up to Day 15 and up to Day 29 respectively. It will be presented by treatment group together with the difference in response rates.

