## 10.6 9-point ordinal scale

Patient State	Descriptor	Score	Abbreviated description
Uninfected	No Clinical or virological evidence of infection	0	Uninfected
Ambulatory	No limitation of activities	1	Amb: No limitations
	Limitation of activities	2	Amb: Limitations
Hospitalized Mild disease	Hospitalized, no oxygen therapy	3	Hosp: No Oxygen
	Oxygen by mask or nasal prongs	4	Hosp: Oxy Mask
	Non-invasive ventilation or high-flow oxygen	5	Hosp: Non-Inv Vent
Hospitalized Severe disease	Intubation and mechanical ventilation	6	Hosp: Intub + Mech Vent
	Ventilation + additional organ support - pressors, RRT, ECMO	7	Hosp: Vent + pressors
Dead	Death	8	Dead

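### SAP 6.2.5 censors deaths in the Kaplan-Meier graph of survival without invasive mechanical ventilation, although the endpoint's definition in 6.2.1 makes death a failure

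*SAP*

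**What the plan says.** The endpoint is fixed in SAP 6.2.1: "Survival without the need for invasive mechanical ventilation at Days 15 and 29: defined by a 9-point ordinal scale score of" less than 6 at all time points. The scale in SAP 10.6 gives 6 to "Intubation and mechanical ventilation", 7 to ventilation with additional organ support, and 8 to death.

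The missing-data rules under 6.2.1 add, for participants who died before Day 29: "The score for death will be imputed for all visits following the death up to and including Day 29".

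The planned numerical result is in SAP 6.2.2: "The numbers and percentages of responders will be calculated up to Day 15 and up to Day 29 respectively", shown by arm with the difference in response rates.

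The planned figure is in SAP 6.2.5, under the same endpoint name: "Kaplan-Meier graphs with separate lines by treatment group will be provided for a graphical presentation". The next sentence sets the censoring rule: "Censoring events will be death and discontinuation from the study". The visible text attaches no log-rank test, hazard ratio or confidence interval to the figure.

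**The concern.** The two rules treat the same participant differently. Someone who dies without ever reaching a score of 6 or 7 fails the endpoint in the table and is censored as event-free in the graph.

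Kaplan-Meier censoring assumes that the person removed would have gone on with the same risk of the event as those still followed. A participant who has died has no later risk of ventilation, and in COVID-19 pneumonia death and the need for ventilation are unlikely to be unrelated. So a curve labelled as survival does not show survival. It shows freedom from ventilation in a hypothetical setting where nobody dies.

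The rule also departs from the rest of the SAP, which gives death the worst outcome on the combined APACHE II score (6.1.8) and on the ordinal scale (6.2.1).

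At stake is what a reader takes from the figure. It can sit above the responder rate for the same endpoint, and it cannot show a difference between arms in deaths that occur without ventilation.

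**Working it through.** **Consistency check.**

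| Participant's course | Responder table (6.2.1, 6.2.2, 10.6) | Graph (6.2.5) |
|---|---|---|
| Ventilated, then survives or dies | Failure (score 6 or 7 reached) | Event at ventilation |
| Dies without prior ventilation | Failure (8 is not below 6) | Censored |
| Alive, never ventilated, followed to Day 29 | Responder | Event-free |

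Only the second row conflicts. No visible text reconciles it.

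**Direction.** At each event time both versions of the curve have the same risk set. Counting deaths as events can only add factors below 1 to the product, so the death-censored curve is never below the composite curve.

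**Size.** The SAP states no event rate, sample size or power for this endpoint, so there is no figure to reproduce. The rates below are assumptions. Let v be the proportion ventilated by Day 29 and d the proportion dying without prior ventilation, with constant cause-specific hazards and no dropout. Day 29 is the horizon because SAP 1.4 says "participants will be observed until Day 29 or discharged from hospital, whichever is sooner", with a Day 29 telephone visit after discharge.

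- Composite event-free proportion: S = 1 - v - d
- Total cumulative hazard: H = -ln(S)
- Death-censored curve at Day 29: KM = exp(-H × v/(v + d))

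Example with v = 20% and d = 10%: S = 0.700, H = 0.357, KM = exp(-0.357 × 20/30) = 0.788. The curve is 8.8 points too high.

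Each cell gives composite / death-censored (excess in points):

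| v | d = 0 | d = 2% | d = 5% | d = 10% | d = 15% |
|---|---|---|---|---|---|
| 10% | 90.0 / 90.0 (0) | 88.0 / 89.9 (1.9) | 85.0 / 89.7 (4.7) | 80.0 / 89.4 (9.4) | 75.0 / 89.1 (14.1) |
| 20% | 80.0 / 80.0 (0) | 78.0 / 79.8 (1.8) | 75.0 / 79.4 (4.4) | 70.0 / 78.8 (8.8) | 65.0 / 78.2 (13.2) |
| 30% | 70.0 / 70.0 (0) | 68.0 / 69.7 (1.7) | 65.0 / 69.1 (4.1) | 60.0 / 68.2 (8.2) | 55.0 / 67.1 (12.1) |

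The excess is nearly the whole of d.

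**Contrast between arms.** Three assumed cases show the range:

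- Same d in both arms (10%), v = 10% against 20%: composite 80.0% against 70.0%, a gap of 10.0 points; curves 89.4% against 78.8%, a gap of 10.6. The bias largely cancels.
- Same v (12%), d = 10% on SoC against 4% on DFV890: composite 78% against 84%, a gap of 6 points; curves 87.3% against 87.7%, a gap of 0.4. The difference is hidden.
- v = 10%, d = 10% in one arm against v = 12%, d = 4% in the other: composite 80% against 84%; curves 89.4% against 87.7%. The order reverses.

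**Ten-participant example.** Ventilation on Days 5 and 9, deaths without ventilation on Days 7 and 12, six event-free to Day 29. Deaths censored: 9/10 × 7/8 = 78.8%. Deaths as events: 9/10 × 8/9 × 7/8 × 6/7 = 60.0%, which equals the responder proportion of 6/10.

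**The case against.** The strongest reply is that this is one descriptive graph. No test or decision rests on it, and the numerical result for the endpoint is the responder rates, which count deaths as failures. That stands, and it limits the weight of the point.

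Mortality also remains visible elsewhere. Score 8 appears by arm in the Day 15 and Day 29 bar charts and in the heat maps (6.2.2), worst-case imputations for death are counted by arm (6.1.2), and deaths from SAEs are tabulated (7.2.6). A reader might infer that the rule conceals mortality from the trial's report; it does not. The loss is confined to this figure.

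A reader might also infer that the curve drops half of the endpoint. The documents do not support that. Deaths after ventilation are already events at the time of ventilation, so only deaths without a prior score of 6 or 7 are lost, and their share is unknown. Nor does a censored participant stay at risk: that person leaves the risk set, and the fault lies in the assumption made about their later risk.

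Finally, it can be said that time to ventilation was what the authors meant. The endpoint name and definition say survival, so on that reading the figure is mislabelled, and with death as a competing event a Kaplan-Meier curve still does not give the proportion free of ventilation.

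**Conclusion.** The censoring rule is wrong as written, because it contradicts the definition of the endpoint that the graph is meant to display. The direction is certain: where anyone dies unventilated, the curve can only be too high. The size depends on rates that the SAP does not give. Under constant hazards, no dropout and 10-30% ventilated, the Day 29 excess runs from zero when nobody dies without ventilation, through about 2 points at 2% and 8-9 points at 10%, to 12-14 points at 15%. The effect on the contrast between arms ranges from slight, when such deaths are balanced, to hiding or reversing a difference when they are not.

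This should be corrected, but it does not threaten the trial's main conclusions. A reader might take it to mean that the secondary endpoint result itself is biased. That does not follow: the responder rates, their difference and the primary APACHE II analysis do not use this rule. Nor must graph and table disagree on account of deaths; they do so only if some participants die without prior ventilation.

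**What to change.** In SAP 6.2.5, define the event as the first of an ordinal score of 6 or more or death from any cause. Censor only participants who are alive and event-free, at study discontinuation or at Day 29.

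If time to ventilation alone was intended, rename the figure and replace the Kaplan-Meier curve with cumulative incidence of ventilation, treating death as a competing event.

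A small mismatch with the table may remain. The rules under 6.2.1 carry the last ordinal score forward for living participants with missing data, so a living dropout last scored below 6 counts as a responder in the table but is censored in the curve. A footnote to the figure can say so.

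The cost is one sentence of SAP text and one change to the event flag, with no new data. It should be made before database lock, since choosing the event definition later in an open-label trial would be open to question.
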